16.4 Recruitment of Subjects

It is intended that potential subjects for this study will be identified amongst patients referred to the clinic for further treatment and diagnosing. Potentially suitable subjects will be approached by the investigating team at the site to ascertain whether they would be interested in participating in the study. Interested subjects will be provided with an information sheet and undergo consenting procedures prior to any other study procedures.

16.4.1 Subject Participation Card

A study participation card will be provided to each subject in the study. The card will indicate that the subject is participating in a clinical trial and give the name and contact details of the sponsor and the investigator/study site. The subjects will be asked to retain this card while they are participating in the trial and show it to any other medical practitioners they consult during this time. They will be advised to contact the investigator/study site if there are any questions.

16.5 Withdrawal

16.5.1 Subject may decide to withdraw

Subjects will be informed that they have the right to withdraw from the study at any time and for any reason without prejudice to his or her future medical care by the physician or the institution.

Subjects who prematurely discontinued from the study will not be replaced. The date for premature discontinuation will be recorded in the subject's source documents and electronic Case Report Form (eCRF).

If a subject is discontinued at any time after entering the study, the investigator should make a reasonable effort to ascertain the reason(s) while fully respecting the subject's rights, as a subject is not obliged to give a reason(s) for withdrawing. The investigator or site personnel should make every effort to contact the subject to assess his or her status and complete the termination page on the eCRF. In the case of subject discontinuation, the procedures described for the End of Study will be applied, where possible.

16.5.2 Discontinuation of Individual Subjects

The investigator may also withdraw a subject from the treatment or the study for any of the following reasons:

- If a subject who does not meet enrolment criteria is inadvertently enrolled
- · Enrolment in any other clinical trial with a study drug
- In case of severe worsening of symptoms, the investigator will be able to provide joint injections with corticosteroid as rescue medication. The use of local joint injections will be at the discretion of the investigator. The IMP/placebo treatment will continue as planned
- If the subject, for any reason, requires treatment with another therapeutic agent (rescue medication not included) that has been demonstrated to be effective for treatment of the study indication, discontinuation from the study occurs prior to the introduction of the new agent
- For medical or safety reasons
- If a female becomes pregnant

In case of early subject discontinuation and the reason for discontinuation (if it is known) will be registered in the eCRF and source documentation.

Protocol Code Number: SynAct-CS002

17 TREATMENT PLAN AND PROCEDURES

17.1 Subject Identification

Each subject who signs the informed consent will be assigned a unique subject number (01-1001 site 1, 02-1001 etc.), which will be used as the subject's identification in the eCRF and on all source documentation throughout the study. The screened subjects will be consecutively numbered, and the first available number, as listed in the eCRF, will be used. In the case of re-screening, a new screening number will be allocated. Subjects who are assigned a subject number but fails the randomization will be registered as a screen failure on the screening list and in the eCRF.

17.2 Randomization and Treatment Assignment

Following a successful screening evaluation, eligible subjects will be randomized into the study.

Each subject will be assigned a unique randomization number in ascending order, based on a list provided by HB Medical, and assigned a protocol specified drug treatment. Randomization numbers should be assigned according to the list and should not be omitted or reused.

An external statistician will prepare the randomization list and emergency code envelopes. The randomization list will be kept strictly confidential, filed securely by HB Medical (or designee), and accessible only to authorized persons per HB Medical's Standard Operating Procedures (SOPs) until the time of unblinding. A copy of the list is sent to PharmaLex Denmark, who is handling the pharmacovigilance.

The study treatment will be unknown to the Clinical Research Organization (CRO) and sponsor personnel associated with the study, all subjects, the investigator, and all site personnel except for the unblinded pharmacist(s) and personnel at HB Medical and the unblinded statistician responsible for preparing the randomization list.

18 INVESTIGATIONAL PRODUCT(S)

The individual study drug information is presented in the below tables.

Table 1, Test Treatment

Name	AP1189
Dosage strength	50 mg, 100 mg
Formulation	Powder
Route of	Oral
Supplier	SynAct Pharma

Table 2, Reference Treatment

Protocol Code Number: SynAct-CS002

Name	Placebo
Dosage strength	0 mg
Formulation	Powder
Route of	Oral
Supplier	SynAct Pharma

A description of the pharmaceutical properties and composition of the formulation of AP1189 is provided in the IB.

18.1 Description of AP1189 Investigational Product

18.1.1 Nomenclature

IUPAC: E-N-[trans-3-{1-(2-nitrophenyl)-1H-pyrrole-2-yl}-allylideneamino] guanidinium acetate

Proprietary: AP1189

18.1.2 Drug Substance

The substance is an acetic acid salt that appears as an odorless, yellow solid.

Structural formula

➤ Molecular formula: C₁₆H₁₈N₆O₄

18.1.3 Basic physical and chemical Characteristics

The molecular weight is 358.35 for the salt and 298.30 for the free base.

18.2 Packaging and Labeling

The sponsor (or designee) will provide HB Medical with study drug. IMP/placebo will be delivered the sites in bottles with screw caps and labeled following all applicable regulatory requirements and Good Manufacturing Practice Guidelines.

The label on the box containing the bottles with IMP will include the following information:

- Study number
- AP1189/ placebo powder in bottle
- Batch number
- Randomization number
- Expiry date
- Storage conditions
- Name and phone number of the responsible investigator

Protocol Code Number: SynAct-CS002

- Sponsor name and address
- For clinical trial use only
- Keep out of reach of children

The label on the bottles containing AP1189/placebo, which is to be dispensed to subjects, will include the following information:

- Study number
- AP1189/ placebo powder in bottle
- Randomization number
- Batch number
- Storage conditions
- Name and phone number of the responsible investigator
- Sponsor name and address
- For clinical trial use only
- Keep out of reach of children

Labels on the box and the bottles will be in the local language.

18.3 Drug Supplies

After receipt of all required documentation, including written approval from the IEC/IRB and CA, HB Medical will supply sufficient study drug/ placebo for the clinical sites to conduct the study, as appropriate.

18.3.1 Drug Accountability

The investigator at each site must maintain adequate records documenting the receipt, use, loss, or other disposition of drug supplies.

The site pharmacist/study nurse (as appropriate per country) will verify that study drug supplies are received intact and in the correct quantities which will be documented by signing and dating the Proof of Receipt. The site pharmacist/study nurse will also sign and date a Proof of Receipt for the corresponding code envelopes. An accurate (running) inventory of study drug will be kept by the site and will include the batch number, date of receipt, subject number, date, and initials of the person who dispense the drug, and finally the date and amount of study drug each subject return to the site. A sample of the Drug Accountability Form, following instructions provided by the monitor, will also be provided to the site pharmacist/study nurse. Accountability of the study drug will be performed and verified by the monitor throughout the study duration.

All unused IMP/placebo must be registered, accounted for, and returned to HB Medical or destroyed per instructions from SynAct Pharma and according to local regulations. The investigator, subinvestigator(s), and/or site pharmacist/study nurse agree not to supply study medication to any persons not enrolled in the study.

Protocol Code Number: SynAct-CS002

18.3.2 Storage and Handling

The IMP/placebo will be stored in a secure limited access area in accordance with required storage conditions. The study pharmacist/investigator at each site will be responsible for the correct storage and handling of the study products.

Both AP1189 and placebo should be stored at room temperature between +15°C and 25°C. All study drug must be protected from light and moisture. They should not be refrigerated or frozen.

18.4 Administration and handling of Study Drug

The study drug will be dispensed four times during a subject's participation in Part 1 and Part 2 respectively; at the Baseline Visit, visit 2, visit 3 and at visit 4. The study drug will be in a box with 8 bottles (study drug for one week's use) containing powder of either AP1189/placebo, a funnel, and a measuring cup.

The subject adds 50 ml of tap water to the powder in the bottle, shakes well for about 1 minute allowing all powder to dissolve and then immediately drink the solution. The subject must rinse the bottle two times with 50 ml water to ensure ingesting all the medicine in the bottle. Between each rinse, the content of the bottle is drunk. Each subject will use one bottle daily during the treatment period.

The subjects will be instructed to take the suspension once daily in the morning about an hour before breakfast during the treatment period. It is up to the subject whether they would like to drink a glass of apple juice immediately after dosing. On the visit days, the medication should first be taken after blood sampling has been done.

At the Baseline Visit, the subject will receive a diary to make daily records of what time the treatment is taken.

The investigator or her/his designee is responsible for explaining the correct use of the study drug and the diary to each subject, and the subjects will receive a written instruction too.

Subjects will be instructed to return empty bottles, unopened bottles, and the diary at each visit.

The effect of food intake on the absorption of AP1189 in the current suspension formulation has not been systematically evaluated. However, it has been shown that the plasma profile of the compound, whether the first meal was served 1 hour or 4 hours post-dosing in the fasting state, is very similar. Further, it has been shown that intake of a glass of apple juice immediately after dosing does not reduce the absorption.

18.5 Blinding

18.5.1 Blinding of Investigational Product

This study is conducted under double-blind conditions primarily to minimize bias in the reporting, collection, and initial assessment of data.

The investigator, study personnel, as well as sponsor personnel involved in the conduct of the study, will be blinded to the study medication. Except in the case of emergency, the study randomization codes will not be available to the above personnel until after the completion of the study and final data review.

Emergency code envelopes, which each investigational site will receive every time they receive a new batch of IMP, will be kept in a secure environment at the individual study site. A code, which reveals the treatment

Protocol Code Number: SynAct-CS002

allocated for a specific subject, may in case of emergency be opened during the study if the choice of treatment depends upon it.

18.5.2 Breaking the Blind

The study blind can be broken if, in the opinion of the investigator, it is in the subject's best interest to know the study drug assignment. SynAct Pharma must be notified before breaking the blind unless identification of the study drug is required for emergency therapeutic measures. If an emergency therapeutic measure is necessary which warranted breaking of the blind, SynAct Pharma must be notified within 24 hours of the blind being broken. The date and reason for blind breaking must be recorded in source documentation.

19 PRIOR AND CONCOMITANT MEDICATION

Prior medications and therapies are taken within 4 weeks prior to the Screening Visit. Concomitant medications are those medications, other than study drug, taken after the Screening Visit. Both prior medications, as well as concomitant medications, will be recorded in the eCRF by generic name.

Any medication or vaccine (including over-the-counter or prescription medicines, vitamins, and/or herbal supplements) that the subject is receiving up to 4 weeks prior to screening or receives at any time during the study will to be recorded along with the reason for use, date(s) of administration including start and end dates, and dosage information including dose, route, and frequency.

19.1 Permitted Medicines

Permitted medications are any medications required per the medical history and not explicitly prohibited by the protocol during the trial. These standard of care medications are part of the subject's previous treatment and will therefore not be provided by the sponsor. Any such medications prescribed or used should be recorded in the eCRF.

19.1.1 Methotrexate (MTX)

All subjects should follow the local guideline for each hospital and/or country for starting treatment with MTX and continue MTX treatment throughout their participation in the study. MTX is not provided by the sponsor, as it is not background treatment but part of the patients' regular treatment.

19.1.1.1 MTX Treatment Instruction in Case of Elevation in Liver Enzymes

It is recommended with more frequent blood test in case of elevation of liver enzymes.

Transaminase Increase:

Laboratory Value	Action
ALT and/or AST increases	IMP and MTX remains unchanged.
up to > 1 to ≤ 3 x Upper Limit of Normal (ULN)	It is recommended with more frequent blood test in case of elevation of liver enzymes.
And bilirubin is within the normal range	

Protocol Code Number: SynAct-CS002

Laboratory Value	Action
ALT and/or AST increases > 3 to ≤ 5 x ULN	Pause IMP dosing until ALT and/or AST < 3 x ULN and follow recommendations above for > 1 to < 3 x ULN
And bilirubin is within the normal range	Upon normalization of ALT and/or AST, IMP resumes For persistent increases > 3 x ULN, discontinue IMP
ALT and/or AST > 5 x ULN	MTX and IMP discontinue
Bilirubin > normal range	MTX and IMP treatment discontinue

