7 PROTOCOL SYNOPSIS

Protocol title	A double-blind, multi-center, two-part, randomized, placebo-controlled study of the safety, tolerability, and efficacy of 4 weeks of treatment with AP1189 in early rheumatoid arthritis (RA) patients with active joint disease
Protocol no	SynAct-CS002
Clinical phase	Ila
Estimated study duration	Study duration: 18 months Study participation for each subject is estimated to 10 weeks
Study design	A multicenter, two-part, randomized, double-blind, placebo-controlled, 4-week study with repeated doses of AP1189. The study population will consist of newly diagnosed subjects with severe active RA (CDAI (Clinical disease activity score) > 22) who are to start up-titration with methotrexate (MTX).
	Part 1: The subjects will be randomized into:
	 Group A: AP1189 dose 50 mg (min. 8 subjects) or Group B: placebo (min. 4 subjects)
	Steering Committee (SC) meeting
	 Group C: AP1189 dose 100 mg (min. 8 subjects) or Group D: placebo (min. 4 subjects)
	INTERIM ANALYSIS
	Part 2: All subjects will be randomized into either design 1, 2 or 3 based on data from the interim analysis.
	 Design 1: AP1189 dose 50 mg (44 subjects) or placebo (22subjects) plus MTX (10-25 mg) weekly Design 2: AP1189 dose 100 mg (44 subjects) or placebo (22 subjects) plus MTX (10-25 mg) weekly Design 3: Continue with the same doses as in Part 1, in a 1:1:1 ratio (AP1189 50 mg (22 subjects), AP1189 100 mg (22 subjects) or

Protocol Code Number: SynAct-CS002

	placebo (22 subjects)) plus MTX (10-25 mg) weekly
Study sites	The study is to be conducted at sites in Europe and Moldova
Treatment duration	Multiple dose administration consisting of once- daily dosing from Day 1 to Day 28, preceded by a screening period of up to 2 weeks before the first dosing. A 4 weeks safety follow-up period will follow the last dose administration
Study population	Subjects with severe active RA, defined as CDAI > 22, who are about to begin up-titration with MTX
Study objectives	Primary safety objective: • To compare the safety of AP1189 against placebo by evaluating adverse events (AEs), serious adverse events (SAEs), and laboratory abnormalities
	 Primary efficacy objective: Effect of AP1189 vs. placebo in subjects with severe active RA (CDAI > 22), undergoing up-titration with MTX, by showing a change in CDAI from severe (CDAI > 22) to moderate (CDAI ≤ 22) after 4 weeks treatment compared to baseline

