21.1.9.3 Biochemistry

Sodium, potassium, chloride, calcium, glucose, creatinine, urea, albumin, unconjugated and total bilirubin, aspartate transaminase (AST), alanine transaminase (ALT), alkaline phosphatase (ALP), gamma-glutamyl transferase (GGT) and INR. The biochemistry blood samples will be taken at all visits. A serum β -HCG pregnancy test will be taken at screening (dipstick pregnancy test at all other visits).

Protocol Code Number: SynAct-CS002

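### In the > 3 to ≤ 5 x ULN liver-enzyme row, two restart conditions for paused IMP conflict for values between 1 and 3 x ULN, and neither clearly requires both enzymes to have recovered

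*Protocol*

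**What the plan says.** The liver table is in Protocol 19.1.1.1. Its first row covers ALT and/or AST above 1 and up to 3 x ULN with normal bilirubin. The action there is "IMP and MTX remains unchanged", with more frequent blood tests recommended.

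The second row covers ALT and/or AST above 3 and up to 5 x ULN, again with the condition "And bilirubin is within the normal range". Its action cell contains three instructions:

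- "Pause IMP dosing until ALT and/or AST < 3 x ULN and follow recommendations above", where the recommendations meant are those for the band above 1 and below 3 x ULN;
- "Upon normalization of ALT and/or AST, IMP resumes";
- "For persistent increases > 3 x ULN, discontinue IMP".

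The remaining rows stop both MTX and IMP for ALT and/or AST above 5 x ULN or for bilirubin above normal. Neither the current protocol text nor the SAP defines normalization or says which restart condition takes precedence.

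**The concern.** The first instruction ends the pause once the value is below 3 x ULN and sends the reader to a band in which IMP continues. The second makes normalization the point of restart. The table uses the normal range in its usual sense for bilirubin, and its first row treats anything above 1 x ULN as an increase that merits extra testing. On that usage, a site that waits for the reference range is following the words. A site that restarts at 2 x ULN is following them too.

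The and/or wording suits a trigger, where either enzyme should count. It does not suit a recovery test, because it does not say whether both enzymes must have come down.

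What is at stake is consistent re-exposure to IMP after a liver signal. Protocol 11.3.2 asks for careful monitoring of liver values, laboratory abnormalities are part of the primary safety endpoint (13.1), and 15.10 gives liver parameters particular weight in the choice of the Part 2 design.

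**Working it through.** The plan gives no figure to reproduce. The check compares the two conditions across the range of values, then bounds the difference in doses.

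**Step 1: the two conditions side by side.** Take a paused subject with normal bilirubin, and let the value be the higher of ALT and AST. Read normalization as ≤ 1 x ULN.

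| Value | Below-3 x ULN condition | Normalization condition |
|---|---|---|
| ≤ 1 x ULN | resume | resume |
| > 1 to < 3 x ULN | resume | stay paused |
| exactly 3 x ULN | stay paused | stay paused |
| > 3 to ≤ 5 x ULN | stay paused; discontinue if persistent | stay paused; discontinue if persistent |

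The conflict is confined to the second line. If normalization is instead read as a return below 3 x ULN, the two columns agree throughout. The text does not say this.

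**Step 2: the and/or wording.** Take ALT 4 x ULN and AST 2 x ULN. ALT puts the subject in the pause row. If the recovery test is read with or, AST already meets the below-3 x ULN condition on the day of the pause. If both enzymes, or the enzyme that triggered the pause, must recover, it is not met.

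**Step 3: illustrative bound on doses for one affected subject.** Inputs:

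- Dosing: "daily dosing from Day 1 to Day 28" (Protocol synopsis), so 28 doses.
- Draws: "The biochemistry blood samples will be taken at all visits" (Protocol 21.1.9.3), nominally days 7, 14, 21 and 28 (section 20.1).
- Visit days: "On the visit days, the medication should first be taken after blood sampling has been done" (section 18.4), so a restart on a visit day includes that day's dose.

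Assumptions: visits fall on the nominal day, results are available the same day, and only scheduled draws are used.

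A restart on day d gives 28 − d + 1 = 29 − d further doses. Let d be the first draw below 3 x ULN and e the first draw at or below 1 x ULN. The readings differ by (29 − d) − (29 − e) = e − d doses, or by 29 − d if the value never reaches 1 x ULN by Day 28.

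- Pause on day 7, d = 14: 29 − 14 = 15 doses under the below-3 reading. The difference is 0 if e = 14, 7 if e = 21, 14 if e = 28, and 15 if never (15/28 = 53.6%).
- Pause on day 14, d = 21: 29 − 21 = 8 doses. The difference is 0, 7 or at most 8 (8/28 = 28.6%).
- Pause on day 21, d = 28: 29 − 28 = 1 dose. The difference is 0 or 1 (1/28 = 3.6%).

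Every range starts at 0, and each upper end needs a subject who falls below 3 x ULN but never reaches 1 x ULN. An earlier unscheduled retest would move d forward and raise the upper end by one dose per day. The documents give no retest interval, so no figure is attached to that case.

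**The case against.** The strongest reply is that the row largely explains itself. The pause starts above 3 x ULN, is said to end below 3 x ULN, and becomes permanent if values stay above 3 x ULN. The reference back to the continue-dosing band would serve little purpose if the subject had to wait for the reference range, and that reading leaves no rule for values that settle between 1 and 3 x ULN. This stands: 3 x ULN is the more likely intention. It does not remove the problem, because the normalization sentence is still there as a separate restart instruction.

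On and/or, the reply is that a subject with ALT at 4 x ULN still meets the trigger, so no sensible reader would end the pause because AST is low. That is fair as a prediction of practice. The wording still does not state the requirement, and naming both enzymes costs nothing.

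A reader might infer that the looser reading exposes subjects at enzyme levels the protocol regards as unsafe for dosing. The documents do not support that. A restart below 3 x ULN falls within the range where the first row already leaves IMP unchanged, and the stops above 5 x ULN, for raised bilirubin and for persistent values above 3 x ULN are unaffected. Investigators may also order extra tests (section 21) or withdraw a subject for safety (16.5.2). Neither provision says when a paused subject may restart.

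**Conclusion.** The row is wrong as written: it gives two restart conditions that conflict above 1 and below 3 x ULN on the ordinary meaning of normalization, and it does not require both enzymes to have recovered. It is a minor correction to a safety instruction.

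The reach is limited to subjects whose IMP is paused under this row. Their number is unknown and probably small. In Phase I Part IV (Protocol 10.1.6), aminotransferase rises of up to 3.6x occurred in five subjects, all in the 200 mg cohort, a dose not used here, and two of the five were on placebo. That is only a rough guide, because those were healthy volunteers and every subject here is starting MTX.

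The dose differences above are illustrative upper ends for a single subject and should not be used to grade the point. A reader might infer from them that up to half of the planned exposure is in doubt. The documents do not support this: they give no frequency of pauses, and the difference is zero whenever the first value below 3 x ULN is also within the reference range. No stated statistical figure, analysis set or endpoint definition depends on the row.

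**What to change.** Delete the sentence that ties the restart to normalization and make the action for this row:

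*Pause IMP; resume when both ALT and AST are < 3 x ULN and bilirubin is within the normal range, with more frequent blood tests; for persistent ALT or AST > 3 x ULN, discontinue IMP.*

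This leaves the discontinuation threshold as it is. The bilirubin condition matches the existing bilirubin stop.

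The sponsor should first confirm which threshold was meant. If full normalization was intended, the wording above would loosen the rule. The row should then require both enzymes to be ≤ 1 x ULN and add an instruction for values that settle between 1 and 3 x ULN.

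The cost is a small protocol amendment, submitted and where necessary approved under Protocol 26.1.1, plus a notice to sites. It can help only subjects not yet treated; SAP 3.7 records that the Part 1 interim analysis has already been done. Data collection, sample size and planned outputs do not change. The SAP already lists the daily IMP diary (section 4) and tabulates the action taken with study drug for adverse events (7.10).
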